7.7.2 Pregnancies in Female Partners of Male Patients

Male patients will be instructed through the Informed Consent Form to immediately inform the investigator if their partner becomes pregnant during the study or within 5 months after the last dose of study drug. A Pregnancy Report eCRF should be completed by the investigator immediately (i.e., no more than 24 hours after learning of the pregnancy) and submitted via the EDC system. Attempts should be made to collect and report details of the course and outcome of any pregnancy in the partner of a male patient exposed to study drug. The pregnant partner will need to sign an Authorization for Use and Disclosure of Pregnancy Health Information to allow for follow-up on her pregnancy. Once the authorization has been signed, the investigator will update the Pregnancy Report eCRF with additional information on the course and outcome of the pregnancy. An investigator who is contacted by the male patient or his pregnant partner may provide information on the risks of the pregnancy and the possible effects on the fetus to support an informed decision in cooperation with the treating physician and/or obstetrician.

In the event that the EDC system is unavailable, follow reporting instructions provided in Section 7.7.1.

7.7.3 Congenital Anomalies/Birth Defects and Abortions

Any congenital anomaly/birth defect in a child born to a female patient exposed to study drug or the female partner of a male patient exposed to study drug should be classified as a serious adverse event, recorded on the Adverse Event eCRF, and reported to Genentech immediately (i.e., no more than 24 hours after learning of the event; see above). Abortion, whether accidental, therapeutic, or spontaneous should be reported in the same fashion (because Genentech considers spontaneous abortions to be medically significant events).

7.8 Adverse Events Monitoring

Refer to the Data Safety Monitoring Plan, located in Appendix 2

7.9 Expedited Reporting

7.9.1 Reporting to the Data and Safety Monitoring Committee

If a death occurs during the treatment phase of the study or within 30 days after the last administration of the study drug(s) and it is determined to be related either to the study drug(s) or to a study procedure, the Investigator or his/her designee must notify the DSMC Chair (or qualified alternate) within 1 business day of knowledge of the event. The contact may be by phone or e-mail.

7.9.2 Reporting to UCSF Institutional Review Board

The UCSF PI must report events to the UCSF IRB according to institutional guidelines.

UCSF IRB website for guidance in reporting adverse events: <https://irb.ucsf.edu/adverse-event>

The PI at each participating site is responsible for reporting events to the IRB of record according to IRB guidelines.

The sponsor (UCSF) will be responsible for the distribution of safety information to participating investigators, where relevant, in accordance with local regulations.

7.9.3 Expedited Reporting to the Food and Drug Administration

If the study is being conducted under an IND, the Sponsor-Investigator is responsible for determining whether or not the suspected adverse reaction meets the criteria for expedited reporting in accordance with Federal Regulations (21 CFR §312.32).

The Investigator must report in an IND safety report any suspected adverse reaction that is both serious and unexpected. The Sponsor-Investigator needs to ensure that the event meets all three definitions:

- Suspected adverse reaction
- Unexpected
- Serious

If the adverse event does not meet all three of the definitions, it should not be submitted as an expedited IND safety report.

The timeline for submitting an IND safety report to FDA is no later than **15 calendar days** after the Investigator determines that the suspected adverse reaction qualifies for reporting (21 CFR 312.32(c)(1)).

Any unexpected fatal or life-threatening suspected adverse reaction will be reported to FDA no later than **7 calendar days** after the Investigator's initial receipt of the information (21 CFR 312.32(c)(2)).

Any relevant additional information that pertains to a previously submitted IND safety report will be submitted to FDA as a Follow-up IND Safety Report without delay, as soon as the information is available (21 CFR 312.32(d)(2)).

7.9.4 Expedited Reporting to Genentech

Investigators will be responsible for collecting all protocol-defined Adverse Events (AEs)/Serious Adverse Events (SAEs), pregnancy reports (including pregnancy occurring in female partner of a male study subject), other Special Situation reports, AESIs and Product Complaints with an AE where the patient has been exposed to Genentech Product. The completed Medwatch report should be sent via fax or email to Genentech Drug Safety at:

Fax: [REDACTED]

Email: [REDACTED]

And all Product Complaints without an AE should be reported via:

PC Hotline Number: [REDACTED] (M-F: 5 am to 5 pm PST)

Investigators must report all the above mentioned single case reports adequately to Genentech on a MedWatch form within one (1) business day of the awareness date

- Relevant follow-up information should be submitted to Genentech Drug Safety as soon as it becomes available.
- All Non-serious Adverse Events originating from the Study will be forwarded in a quarterly report Genentech.

7.9.5 Case Transmission Verification of Single Case Reports

The Sponsor agrees to conduct the Case Transmission verification to ensure that all single case reports have been adequately received by Genentech via Sponsor-Investigator emailing Genentech a monthly line-listing documenting single case reports sent by Sponsor-Investigator to Genentech in the preceding time period.

The monthly line-listing will be exchanged within seven (7) calendar days of the end of the agreed time period. Confirmation of receipt should be received within the time period mutually agreed upon.

If discrepancies are identified, the Sponsor and Genentech will cooperate in resolving the discrepancies. The responsible individuals for each party shall handle the matter on a case-by-case basis until satisfactory resolution. The sponsor shall receive reconciliation guidance documents within the 'Activation Package'.

Following Case Transmission Verification, single case reports which have not been received by Genentech shall be forwarded by Sponsor-Investigator to Genentech within five (5) calendar days from request by Genentech.

At the end of the study, a final cumulative Case Transmission Verification report will be sent to Genentech.

For questions related to safety reporting, please contact Genentech Drug Safety:

Tel: [REDACTED]

Fax: [REDACTED] or [REDACTED]

7.9.6 MedWatch 3500A Reporting Guidelines

In addition to completing appropriate patient demographic and suspect medication information, the report should include the following information within the Event Description (section 5) of the MedWatch 3500A form:

- Protocol description (and number, if assigned)
- Description of event, severity, treatment, and outcome if known
- Supportive laboratory results and diagnostics
- Investigator's assessment of the relationship of the adverse event to each investigational product and suspect medication

7.9.7 Follow-up Information

Additional information may be added to a previously submitted report by any of the following methods:

- Adding to the original MedWatch 3500A report and submitting it as follow-up
- Adding supplemental summary information and submitting it as follow-up with the original MedWatch 3500A form
- Summarizing new information and faxing it with a cover letter including patient identifiers (i.e. D.O.B. initial, patient number), protocol description and number, if assigned, brief adverse event description, and notation that additional or follow-up information is being submitted (The patient identifiers are important so that the new information is added to the correct initial report)

Occasionally Genentech may contact the reporter for additional information, clarification, or current status of the patient for whom an adverse event was reported. For questions regarding SAE reporting, you may contact the Genentech Drug Safety representative noted above or the MSL assigned to the study. Relevant follow-up information should be submitted to Genentech Drug Safety as soon as it becomes available and/or upon request.

MedWatch 3500A (Mandatory Reporting) form is available at
<http://www.fda.gov/medwatch/getforms.html>

7.9.8 Aggregate Reports

IND Annual Reports: All IND annual reports submitted to the FDA by the Sponsor-Investigator should be copied to Genentech. Copies of such reports should be emailed to Genentech Drug Safety:

Genentech Drug Safety CTV mail box: [REDACTED]

Other Reports: The Sponsor-Investigator will forward a copy of the Final Study Report to Genentech upon completion of the Study.

7.9.9 Study Close-Out

Any study report submitted to the FDA by the Sponsor-Investigator should be copied to Genentech. This includes all IND annual reports and the Clinical Study Report (final study report). Additionally, any literature articles that are a result of the study should be sent to Genentech. Copies of such reports should be mailed to the assigned Clinical Operations contact for the study:

[REDACTED]
And to Genentech Drug Safety CTV oversight mail box at: [REDACTED]

7.9.10 Queries

Queries related to the Study will be answered by Sponsor-Investigator. However, responses to all safety queries from regulatory authorities or for publications will be discussed and coordinated between the Parties. The Parties agree that Genentech shall have the final say and control over safety queries relating to the Product. Sponsor-Investigator agrees that it shall not answer such queries from regulatory authorities and other sources relating to the Product independently but shall redirect such queries to Genentech.

Both Parties will use all reasonable effort to ensure that deadlines for responses to urgent requests for information or review of data are met. The Parties will clearly indicate on the request the reason for urgency and the date by which a response is required.

7.9.11 Safety Crisis Management

In case of a safety crisis, e.g., where safety issues have a potential impact on the indication(s), on the conduct of the Study, may lead to labeling changes or regulatory actions that limit or restrict the way in which the Product is used, or where there is media involvement, the Party where the crisis originates will contact the other Party as soon as possible.

The Parties agree that Genentech shall have the final say and control over safety crisis management issues relating to the Product. Sponsor-Investigator agrees that it shall not answer such queries from media and other sources relating to the Product but shall redirect such queries to Genentech.

7.9.12 Compliance with Pharmacovigilance Agreement/Audit

The Parties shall follow their own procedures for adherence to AE reporting timelines.

Each Party shall monitor and, as applicable, request feedback from the other Party regarding AE report timeliness in accordance with its own procedures. The Parties agree to provide written responses in a timely manner to inquiries from the other Party regarding AE reports received outside the agreed upon Agreement timelines. If there is any detection of trends of increasing or persistent non-compliance to transmission timelines stipulated in this Agreement, both Parties agree to conduct ad hoc or institute a regular joint meeting to address the issue.

In case of concerns related to non-compliance of processes, other than exchange timelines, with this Agreement, the Parties will jointly discuss and collaborate on clarifying and resolving the issues causing non-compliance. Every effort will be made by the non-compliant Party to solve the non-compliance issues and inform the other Party of the corrective and preventative actions taken.

Upon justified request, given sufficient notice of no less than sixty (60) calendar days, an audit under the provisions of this Agreement can be requested by either Party. The Parties will then discuss and agree in good faith upon the audit scope, agenda and execution of the audit. The requesting Party will bear the cost of the audit.

8 Statistical Considerations and Evaluation of Results

8.1 Determination of Sample Size and Power Calculation

Cohort A

Multi-dose phase: With 6 patients in each cohort, there will be 80% of power to detect the effect size of 1.5 at significance level of 0.1. For the lowest dose level, a 2-fold increase from pre-treatment to post- treatment is expected, if at the higher dose level, there is more than 3-fold increase, assuming the standard deviation equals 1, then there will be 80% power to detect significant treatment effect on the intratumoral immune response.

Expansion phase: Data from a study of intravesical valrubicin chemotherapy in BCG refractory patients³⁴ demonstrated that a 21% CR rate is achievable at 6 months. Assuming a 5% (null) CR rate for untreated patients at 6 months, 15 patients would be required to observe an improvement to a 36% CR rate at 6 months in response to-PD-L1 therapy (effect size = 0.642), at a significance level of 0.1 with 80% power.

Cohort B

A pT0 rate at cystectomy was observed for ~30% of patients treated with immune checkpoint inhibitors monotherapy based on published Phase II clinical trials. In order to observe an improvement from a 30% CR rate (null hypothesis) to 60% CR rate (alternative hypothesis) with the combination of atezolizumab and tiragolumab a total of 21 patients are required in Cohort B assuming a significance level of 0.05 and 80% power.

Using these assumptions, following a lead in safety phase of 6 patients at a combination regimen that is deemed to be safe based on the criteria outlined above, a further 15 patients will be enrolled at the same regimen. This will make a total of 21 patients to be treated in Cohort B with the intended regimen.

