1.8 Rationale for the Study Design

This study will evaluate the pathologic and immunologic changes induced by atezolizumab-based therapy in bladder tissues compared to pretreatment biopsies. This study has two cohorts (Cohort A and Cohort B) and will accrue each cohort sequentially (i.e., Cohort A will fully accrue, then Cohort B).

Cohort A: Atezolizumab Monotherapy

In the initial monotherapy multi-dose phase (Cohort A), the effects of increasing numbers of doses of atezolizumab will be explored. Similarly, the safety, feasibility, and efficacy of administering up to 3 doses of atezolizumab in patients scheduled for cystectomy will also be examined.

- Multi-dose phase (fully accrued as of October 2020): A fixed number of 6 patients will be accrued at each dose level in the multi-dose portion of the study to allow for investigation into the immunologic impact of different cumulative doses of atezolizumab prior to cystectomy. It is unknown whether multiple doses of atezolizumab are necessary to achieve a complete response or a durable remission as opposed to a single dose, and accrual of 6 patients at each dose level will allow for a preliminary estimate of the efficacy of each cumulative dose level. The safety profile of atezolizumab is well established from multiple Phase I - III studies, and treatment related Grade 3 or 4 toxicities were rare. The multi- dose portion may better inform future studies of neoadjuvant atezolizumab and potentially allow for shorter neoadjuvant courses to be administered.

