2.1 Primary Objectives and Endpoints

Cohort A (Atezolizumab monotherapy):

1. Multi-dose cohorts: To assess the intratumoral immune response associated with increasing numbers of Atezolizumab treatments.
 - Endpoint: CD3+ T cell count/ μm^2 between the pretreatment biopsy and the cystectomy tissue following single and multiple neoadjuvant Atezolizumab infusions.
2. Expansion cohort: To assess the anti-tumor activity of Atezolizumab as determined by the pathologic T0 rate (pT0N0) at the time of cystectomy.
 - Endpoint: Pathologic T0 rate at the time of cystectomy, defined as the pathologic absence of disease in the bladder after resection (See section 7.1.1).

Cohort B (Atezolizumab + tiragolumab)

1. To assess the safety of neoadjuvant combination treatment with atezolizumab and tiragolumab according to CTCAE v5.0 in a curative intent treatment population of urothelial carcinoma patients undergoing radical cystectomy.
 - Endpoint: The percentage of patients in Cohort B with treatment-related adverse events according to CTCAE v5.0 or treatment-related delays in surgery beyond 12 weeks following administration of neoadjuvant treatment with atezolizumab and tiragolumab.
2. To assess the anti-tumor activity of Atezolizumab + Tiragolumab as determined by the pathologic T0 rate (pT0N0) at the time of cystectomy.
 - Endpoint: Pathologic T0 rate at the time of cystectomy, defined as the pathologic absence of disease in the bladder after resection (See section 7.1.1).

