8.3.2 Analysis of Primary Endpoints

The immunologic effect of activity study therapy within bladder tissue will be measured by a change in the CD3⁺ T cell count/ μm^2 between the pretreatment biopsy and the cystectomy tissue following study therapy administrations. Immunohistochemistry will be performed in the [name] lab at UCSF per established SOPs. Based on prior experience tissue will be designated into 3 distinct compartments: benign epithelium, tumor centers, and tumor interfaces. Tumor interfaces will be defined as fields where malignant and benign epithelium are present. Automatic cell counts for single- and double-stained cells will be determined for each field with color-specific algorithms.

The cell count for each compartment will be reported as the mean for each of the five quantitated fields. Cells of interest will include CD3⁺ T cells, CD3⁺ Ki67⁺ proliferative T cells,

CD4+ FoxP3- helper T cells, CD4+ FoxP3+ regulatory T cells, CD8+ cytotoxic T cells, as well as PD-1 expression on the different lymphocytes. In collaboration with Genentech, PD-L1 expression on both tumor and immune cells within the microenvironment will be assessed.

For each cohort, the change of T cell counts from pre-treatment to post-treatment will be calculated for each compartment as log2 of the ratio of post-treatment vs. pre-treatment counts. If different regimens are used (for example atezolizumab x 3 doses and tiragolumab x 2 doses) two-sample Wilcoxon rank sum test will be used to compare the difference of the change from pretreatment to post-treatment between cohorts to assess if the intratumoral immune response associated with increasing numbers of treatments. No multiple comparison adjustments will be performed.

8.3.2.1 pT0 rate

Point estimates and 95% confidence intervals of pathologic T0 rate at the time of cystectomy as defined in Section 7.1.1 will be obtained for subjects treated with atezolizumab and tiragolumab. Pathologic T0 rate at the time of cystectomy will be compared with the null hypothesis rate (see Section 8.1) separately by using one-sample proportion test.

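### Section 8.1's 80% power for a 2-fold versus more than 3-fold increase does not reproduce as written; on the planned log2 scale, power at 3-fold is about 23-25% two-sided

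*Combined protocol and SAP*

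**What the plan says.** Section 8.1 (Cohort A, multi-dose phase) makes two consecutive power statements. The first says that with 6 patients per cohort "there will be 80% of power to detect the effect size of 1.5 at significance level of 0.1". The second puts this in biological terms. It opens with the rise expected over treatment ("For the lowest dose level, a 2-fold increase from pre-treatment to"). It then attaches the power to the higher dose: "if at the higher dose level, there is more than 3-fold increase, assuming the standard deviation equals 1, then there will be 80% power". The sentence closes by saying what this power is for: "to detect significant treatment effect on the intratumoral immune response".

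Section 8.3.2 sets the analysis scale. The change in T cell count "will be calculated for each compartment as log2 of the ratio of post-treatment vs. pre-treatment counts". For the comparison of regimens, a "two-sample Wilcoxon rank sum test will be used to compare the difference of the change from pretreatment to post-treatment between cohorts".

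This comparison serves the primary objective of the multi-dose phase in section 2.1: "To assess the intratumoral immune response associated with increasing numbers of Atezolizumab treatments". Section 1.8 fixes the size: "A fixed number of 6 patients will be accrued at each dose level in the multi-dose portion of the study".

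Neither 8.1 nor 8.3.2 says on which scale the SD of 1 applies, what the 3-fold increase is relative to, or whether the 0.1 level is one- or two-sided.

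**The concern.** The second statement reads as an illustration of the first, so a 2-fold rise against a 3-fold rise with SD 1 ought to be an effect size of about 1.5. It is not, on either the log2 or the raw fold scale, if both rises are measured from pre- to post-treatment. That is the only reference the text names.

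The sentence also ends by claiming power for a treatment effect, whereas the planned test compares dose levels with each other.

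At stake is the reading of a null result. Section 1.8 says the multi-dose portion may inform later studies and possibly allow shorter courses. A reader told that there was 80% power at 3-fold could take a non-significant comparison as evidence that further doses add little. If the true power is about one in four, that inference is not supported.

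**Working it through.** **Inputs.** From section 8.1: n = 6 per dose level, level 0.1, SD 1, 2-fold at the lowest dose, 3-fold as the threshold at the higher dose, stated power 80%. From section 8.3.2: log2(post/pre), two-sample Wilcoxon rank sum test. Sidedness is not given, so both are shown.

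**Step 1: the plan's own effect-size statement.** The two-sided normal formula gives n = 2(1.645 + 0.842)² / 1.5² = 5.5, i.e. 6 per group, so the sample size reproduces. With exactly 6 per group and d = 1.5, two-sided power is 83% (normal approximation), 78% (t-test) or 74% (Wilcoxon). One-sided it is 91%, 89% or 85%.

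**Step 2: the fold-change example as an effect size** (SD 1).
- log2 scale, both rises from baseline: d = log2(3) - log2(2) = 1.585 - 1 = 0.585.
- Raw fold scale, both from baseline: d = 3 - 2 = 1.0. An effect size of 1.5 there would be 2-fold versus 3.5-fold.
- log2 scale, 3-fold relative to the lowest dose level: d = log2(3) = 1.585, which is 2 × 3 = 6-fold over baseline.

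**Step 3: power.** The t-test uses the noncentral t distribution with 10 degrees of freedom and noncentrality d√(6/2) = 1.732d. The Wilcoxon test uses exact critical values (actual size 0.093 two-sided, 0.090 one-sided) with simulated normal data. Each cell runs from Wilcoxon to t-test.

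| Comparison | d | Two-sided | One-sided |
|---|---|---|---|
| log2, 2- v 3-fold | 0.585 | 23-25% | 34-38% |
| log2, 2- v 4-fold; or raw, 2 v 3 | 1.0 | 45-49% | 60-65% |
| log2, 2- v 5-fold | 1.322 | 65-69% | 78-82% |
| log2, 2- v 5.7-fold (2 × 2^1.5) | 1.5 | 74-78% | 85-89% |
| log2, 3-fold relative to lowest dose | 1.585 | 78-82% | 88-91% |

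**Step 4: what 80% would need.** The required d is 1.544 (t) or 1.626 (Wilcoxon) two-sided, and 1.280 or 1.373 one-sided. Against 2-fold on log2, the higher dose must therefore reach 2 × 2^d: about 5.8- or 6.2-fold two-sided, and 4.9- or 5.2-fold one-sided. Alternatively, 3-fold would suffice if the log2 SD were 0.585/d: 0.38 or 0.36 two-sided, and 0.46 or 0.43 one-sided, instead of 1.

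**Step 5: other readings with both rises from baseline.** Natural logs (d = 0.405) give 16-17% two-sided and 24-27% one-sided. Pooling the two higher dose levels (6 v 12, log2, t-test) gives 30% and 44%. Neither comes near 80%.

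**The case against.** The best counter-argument is that the design calculation is sound and only an illustration is in doubt. That stands: n = 6 for an effect size of 1.5 reproduces from the normal formula.

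It can also be argued that the authors meant a 3-fold ratio between dose levels. On log2, an effect size of 1.5 is a ratio of 2^1.5 = 2.83, so a ratio above 3 slightly exceeds it, and power is 78-82% two-sided. This makes the two sentences agree and may well be what was intended, so a plain miscalculation is not proven. But the reading leaves the stated 2-fold figure with no role and appears nowhere in the text. If it is right, the target is about 6-fold over baseline, which a reader of section 8.1 cannot tell.

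A third reading takes the closing words literally, as a within-cohort test of change from baseline. At 3-fold on log2 with 6 patients, a one-sample t-test has 95% power two-sided. That does meet 80% as a minimum, but it does not reproduce the stated figure and is not the between-cohort test in section 8.3.2.

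Finally, 3-fold is a lower bound, so larger increases have more power. True, but the 80% is attached to that threshold, and on log2 it arrives only at nearly twice the threshold or beyond (two-sided).

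**Conclusion.** The concern holds. The 80% attached to the fold-change example cannot be reproduced from the text as written. With both increases from baseline, SD 1 on log2(post/pre) and 6 per level at 0.1, power at 3-fold is about 23-25% two-sided or 34-38% one-sided. A true 3-fold versus 2-fold difference would be missed about three times in four two-sided, or two in three one-sided, rather than one in five.

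These figures assume normally distributed log2 changes and the baseline comparator. Under the alternative comparator (the lowest dose level), the 80% is approximately right two-sided, but the plan would have to say so.

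The practical weight is small. Section 5.2 records that all 18 multi-dose patients were treated, and section 1.8 gives a separate rationale for the fixed six, so no enrolment decision depends on this. It bears on how the comparison serving this phase's primary objective is interpreted.

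**What to change.** Restate the example in section 8.1, naming the SD scale, the comparator and the sidedness. Which wording applies depends on what was meant:

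- **Both changes from baseline, two-sided:** With 6 patients per dose level and SD 1 on log2(post/pre), a two-sided 0.1-level comparison of two dose levels has about 74% (planned Wilcoxon) to 78% (t-test) power for a 1.5 SD difference, i.e. 2-fold versus about 5.7-fold; for 2-fold versus 3-fold, power is about 23-25%.
- **The same, one-sided:** replace these figures with about 85-89% and 34-38%.
- **3-fold relative to the lowest dose level:** say that this is about 6-fold over baseline, with 78-82% power two-sided (88-91% one-sided).

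Refer to a difference between dose levels rather than a treatment effect, to match section 8.3.2. Optionally, report dose-level differences as fold ratios with confidence intervals, which would show directly what a non-significant result can and cannot exclude.

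The required change is wording in section 8.1 only. Sample size, endpoint, planned test and patients are unaffected. If both changes are from baseline, the stated power for the 3-fold example becomes less favourable.
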